# 2. ABBREVIATIONS

CRF	Case Report Form
GCP	Good Clinical Practice
PI	Principal Investigator at a local centre
R&D	Research and Development department
MRS	Magnetic Resonance Spectroscopy
SPMIC	Sir Peter Mansfield Imaging Centre
E-FP	Early Follicular Phase
L-FP	Late Follicular Phase
LP	Luteal Phase
$W_{max}$	Maximum workload
CRF	Case Report Form
GCP	Good Clinical Practice
PI	Principal Investigator at a local centre
R&D	Research and Development department
MRS	Magnetic Resonance Spectroscopy

#### 3. BACKGROUND AND RATIONALE

## **Background**

In recent years, the activities of female athletes have been increasing. However, the blood concentrations of female hormones change significantly for premenopausal women throughout the menstrual cycle (1). Therefore, since the condition of the body changes with the menstrual cycle, it is necessary to establish a conditioning method that considers the menstrual cycle.

Previous work undertaken by co-investigator at Nippon Sports University (Tokyo) has shown that oxidative stress and serum carnitine, which are physiological indices highly related to fatigue, differ through the menstrual cycle (2,3). In addition, studies suggest that the menstrual cycle influences muscle glycogen utilization during high-intensity intermittent exercise until exhaustion in women with habitual exercise activity (European Journal of Sport Science, under revision). Estrogen promotes increased fat oxidation, sparing muscle and hepatic glycogen, decreasing gluconeogenesis, and increasing the exercise time until exhaustion (4). Progesterone is known to reverse several estrogenic effects, including reducing fat oxidation (5). The amount of glycogen stored in the body, either in liver or muscle, is highly related to fatigue and exercise performance. However, the study of a 30-kg box lifting and transport exercise is the only study of the menstrual cycle and liver glycogen by human (6). Furthermore, the study has compared in the early follicular phases (E-FP) when both of serum estradiol and progesterone concentrations are low with in the luteal phase (LP) when both of serum estrogen and progesterone concentrations are high; however, the LP is characterized by high estradiol and progesterone concentrations, and it is thus not possible to determine the effects of estradiol alone. Therefore, conducting measurements in the late follicular phase (L-FP), when serum estradiol concentrations are high but serum progesterone concentrations are low, is necessary to confirm the effects of estrogen alone.

**Aim:** To investigate the effects of hormonal changes throughout the menstrual cycle on moderate exercise induced liver and muscle glycogen changes in healthy women.

#### 4. PARTICIPANTS

## **Description of study participants**

12 healthy females aged 18-35 with regular menstrual cycle (every 25 - 38 days), who take regular exercise. Participants must have no use of any oral contraceptives or other hormone medications for at least 6 months prior to the experiment.

## **Inclusion criteria**

- Female
- Age 18 35 yrs
- Regular menstrual cycle (every 25 38 days).
- Nullinarous
- Habitually exercising (45 min moderate exercise, brisk walking or jogging, minimum 3 days per week)
- Any ethnicity

#### **Exclusion criteria**

- No history of smoking, chronic diseases.
- No use of any oral contraceptives or other hormone medications for at least 6 months prior to the
  experiment.
- Pregnancy or lactation
- Learning difficulties cognitive impairment, social problems, substance abuse or mental illness which would make it difficult to complete the protocol.

# Recruitment

Participants will be recruited by posters placed in University of Nottingham buildings and staff areas of Queens Medical Centre; an electronic version of the study poster posted on University and local community social

media sites; and information included on the 'Call for participant' web site. The posters will include contact details of a member of the research team, for potential participants to make enquiries.

Those expressing an interest in the study will be sent a copy of the information sheet to read and, if they are then willing to participate, inclusion and exclusion criteria will be checked before an initial visit is arranged. They will be sent details of the initial appointment, along with directions, public transport information, and parking information, by email (or post if required).

It will be explained to all potential participants that entry into the trial is entirely voluntary and that they can withdraw at any time. In the event that they withdraw from the study it will be explained that their data collected up to the point of withdrawal cannot be erased and we will seek consent to use the data in the final analyses where appropriate.

## Screening and eligibility assessment

All volunteers will be assessed to ensure that they are suitable to participate, following the criteria listed in the Inclusion / Exclusion Criteria sections. This will be checked with participants before the initial visit. To limit the demands on potential volunteers, participants will be offered to either come to a separate screening visit prior to the start of the study, or to fill our a screening questions over email with final checks undertaken on the initial visit.

Participants will be asked to complete the general study screening questionnaire and the MR Safety Screening questionnaire. Any individuals with tattoos will also be required to complete a tattoo safety form.

## Information provided to participants and informed consent

An information sheet will be given to the participants, and informed consent will be obtained before any measurements are made and confirmed on the initial visit.

## Participant confidentiality

Each participant will be assigned a unique trial identity code number, which will be used on Case Report Forms (CRFs), other trial documents, MR scans and the electronic database. CRFs will be treated as confidential documents and held securely in a locked cabinet. The investigator will make a separate confidential record of the participant's name, date of birth, and Participant Trial Number (the Trial Recruitment Log), to permit identification of all participants enrolled in the trial in accordance with regulatory requirements and for follow-up as required. This Trial Recruitment Log will be stored securely in a locked cabinet separately from anonymised records. Access to CRFs, database and other records shall be restricted to those personnel approved by the Principal or Lead Investigator, including relevant regulatory authorities, and recorded on the 'Trial Delegation Log'.

All research staff and investigators will endeavour to protect the rights of the trial's participants to privacy and informed consent, and will adhere to the Data Protection Act, 2018. The CRF will only collect the minimum required information for the purposes of the project. Computer held data, including the trial database, will be held securely and password protected. Access will be restricted by user identifiers and passwords (encrypted using a one-way encryption method).

#### 5. STUDY PROCEDURES

## **Study Visits**

The participants will be required to visit the research centre on 5 separate occasions, first for a preliminary setup visit and subsequently at 4 points during the menstrual cycle. Each participant will be assigned a trial identity code number for use on trial documents, samples and the electronic database enabling anonymous linkage of the bio-samples and data collected. At visits 2-5, a blood sample of up to 20ml will be collected by a researcher trained in venepuncture. During exercise visits, participants will be supervised by a researcher trained in basic life support and a qualified first aider will be present in the SPMIC in case participant feels faint or needs to immediately stop for any reason.

[figure not shown]
Participants will instructed to refrain from strenuous exercise on the day before visits, to maintain their normal diets, and to keep a diet diary for 2 days prior to each trial. All Participants consume the same standardized dinner on the evening before each test day, which will consist of a frozen tomato pasta vegetarian ready meal provided by the researchers.

#### VISIT 1 (INITIAL VISIT)

During the 1st visit their maximum workload capacity (Wmax) will be determined using a cycle ergometer. Participants will complete an exercise task for up to 2 hours, undergoing incremental steps of 3-4 minutes at constant speed (60 rpm) starting at 50 Watts and increasing by 25 Watts for at least 6 workloads until the participant cannot continue (exhaustion). Between each workload step, participants will have 3 minutes of rest to prevent early fatigue. Heart rate will be recorded for the last 10 seconds of each workload, averaged and plotted to determine the Wmax.

#### VISITS 2 – 5 (STUDY VISITS)

On the morning of visits 2-5, participants will be instructed to eat a standardized breakfast (2 slices of bread and jam without butter/margarine) at a fixed time, and then arrive at the Sir Peter Mansfield Imaging Centre (SPMIC) to begin scanning 3 hours after consumption, with 30 minutes rest at the SPMIC before initial scan. Baseline measures (Pre-exercise) of liver and muscle glycogen will be taken using 13C MRS along with blood samples for analysis. Each participant will then exercise on the cycle ergometer for 40 - 45 minutes at 70% Wmax based on heartrate which will be measured throughout the exercise (pedal speed kept at 60 rpm, adjusted workload). Immediately after exercise cessation (Post-exercise), participants will undergo 13C MRS measurement of liver and muscle glycogen levels, and blood samples is collected (below). Participants who are unable to complete the exercise regime will be removed from the study and paid and inconvenience allowance proportionally, as outlined in their information sheet and consent form.

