## Discontinuation/ withdrawal of participants from study

Participants may be withdrawn from the trial either at their own request or at the discretion of the Investigator. The participants will be made aware that this will not affect their future care. Participants will be made aware (via the information sheet and consent form) that should they withdraw the data collected to date cannot be erased and may still be used in the final analysis.

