# 6. INTERVENTION(S) & DRUG ADMINISTRATION

# a) Drug/Substance/Intervention 1

Name of drug/ substance/	Moderate exercise
intervention to be used	
Formulation and route of	Wmax determined using incremental workload increases
administration for study	
Dose and route of	60 minutes at 70% maximum heartrate
administration for study	
Duration of treatment for	1 x 60 minute of moderate exercise on each of 4 weekly visits
study	
Licence status of this	N/A
drug/substance	
Usual indication	N/A
Usual dose	N/A
Usual duration of treatment	N/A
Where will drug/ substance be sourced from?	
Where will drug/substance be stored?	
How will drug/substance be dispensed?	

How will the drug/ substance	
be prepared by the	
researchers for use in this	
study?	

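### Removing women who cannot complete the exercise ends collection of their remaining phases after an event linked to glycogen and phase, and the protocol leaves the use of their earlier visits unclear

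*Protocol*

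**What the plan says.** The removal rule closes the description of the study visits (Protocol section 5, Visits 2–5): "Participants who are unable to complete the exercise regime will be removed from the study". It follows the account of a single session, so the natural reading is that failing any one session ends participation. The text speaks of the regime, however, and does not say so outright.

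The background (section 3) links the outcome to the ability to finish: "The amount of glycogen stored in the body, either in liver or muscle, is highly related to fatigue and exercise performance". It credits oestrogen with "sparing muscle and hepatic glycogen, decreasing gluconeogenesis, and increasing the exercise time until exhaustion" and says that progesterone reverses several of its effects.

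Two places deal with data from women who leave. Under Discontinuation/withdrawal (section 5): "Participants may be withdrawn from the trial either at their own request or at the discretion of the Investigator", and participants are told that "should they withdraw the data collected to date cannot be erased and may still be used in the final analysis". Under Recruitment (section 4), after a withdrawal, "we will seek consent to use the data in the final analyses where appropriate". Neither mentions compulsory removal for unfinished exercise.

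The analysis (section 8, Statistics) is an ANOVA F-test on values before and after exercise by week, followed by t-tests. It does not say how a woman with fewer than four weeks enters. Section 8 plans 12 women and states no dropout allowance or replacement.

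The session to be completed is described in two ways: "exercise on the cycle ergometer for 40 - 45 minutes at 70% Wmax based on heartrate" in section 5, and "60 minutes at 70% maximum heartrate" in section 6.

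**The concern.** In a within-woman comparison of phases, each woman is her own control only in the phases in which she is measured. If she is removed because she could not finish, and finishing depends on glycogen and on phase, then the chance of being seen in all phases depends on the outcome and on the factor under study. The women who remain may not represent the 12 enrolled.

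Two losses should be kept apart. Visits after removal are never made, and no analysis plan can recover them. Visits before removal exist, and whether they count depends on a data rule that the protocol leaves unclear and on whether the ANOVA tolerates missing weeks. With 12 women, each loss is a noticeable share of the data.

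**Working it through.** **No figure to reproduce.** Section 8 says that a formal calculation was not possible and calls 12 a safe estimate, without power or formula.

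**Inputs from the protocol.** 12 women, 4 exercise visits each, significance level 0.05 (two-sided assumed). Cited muscle glycogen depletion: follicular 46.4 ± 8.4%, luteal 21.2 ± 16.3%; difference 46.4 − 21.2 = 25.2 points.

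**Assumed, because not given.** Non-completion per session q = 5% or 10%, independent between sessions; correlation r between phases from 0 to 0.7; muscle figures standing in for liver.

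**1. Women and visits lost**

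- Women completing all four sessions: 12(1 − q)⁴. At 5%, 12 × 0.95⁴ = 9.8; at 10%, 12 × 0.90⁴ = 7.9.
- Completed visits: 12 × Σ(1 − q)ᵏ, k = 1 to 4. At 5%, 42.3; at 10%, 37.1; out of 48.
- Completed visits of women later removed: 42.3 − 4 × 9.77 = 3.2; 37.1 − 4 × 7.87 = 5.6. A complete-case analysis would leave these unused.
- Visits never attempted (48, less completed visits, less the failed sessions): 48 − 42.3 − 2.2 = 3.5; 48 − 37.1 − 4.1 = 6.8 (6.7 before rounding). No analysis recovers these.

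**2. Precision**

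Detectable standardised paired difference at 80% power (noncentral t): 0.89 SD at n = 12, 1.00 at n = 10, 1.16 at n = 8.

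For the cited effect, the SD of the difference is √(8.4² + 16.3² − 2r × 8.4 × 16.3), which is 18.34 at r = 0 and 12.02 at r = 0.7. Power of the paired t-test, over that range of r:

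| Effect | n = 12 | n = 8 |
|---|---|---|
| Full, 25.2 points | 99.1% to >99.9% | 91.3% to 99.9% |
| Half, 12.6 points | 58% to 91% | 39% to 72% |

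**3. Selection**

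Suppose the two women with the greatest follicular depletion are lost. The two largest of 12 standard normal values sum to about 2.745 on average, so the other ten average −2.745/10 = −0.2745 SD. The follicular mean falls by 0.2745 × 8.4, and the luteal mean by 0.2745 × r × 16.3. The contrast therefore shifts by −0.2745 × (8.4 − 16.3r):

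- r = 0: −0.2745 × 8.4 = −2.3 points
- r = 0.5: −0.2745 × 0.25 = −0.07, about 0
- r = 0.7: −0.2745 × (−3.01) = +0.8 points

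The sign changes at r = 8.4/16.3 = 0.52.

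A simulation with non-completion made likelier by deeper follicular depletion, from a weak link to near-deterministic removal, agrees. At r = 0 the difference of 25.2 falls to 24.8–23.5 if 10% are removed and to 24.0–21.0 if 30% are. At r = 0.5 it stays at 25.1–25.2.

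**4. The data rules side by side**

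Discontinuation allows data collected so far to be used and covers withdrawal by the investigator. Recruitment makes use depend on consent being sought. The removal rule is silent. Whether a removed woman's earlier visits are analysed cannot be settled from these three places.

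**The case against.** A reader might infer that the valid visits of removed women are thrown away. The documents do not support that. The removal sentence says nothing about the data set, and both the withdrawal and the recruitment text foresee use of data already collected. Nor does section 8 specify complete cases or a particular repeated-measures procedure. The separate t-tests on change within each week can use every available visit, and a statistical analysis plan may settle how incomplete women are handled. This stands: discarding is a consequence of one conventional form of the ANOVA, not a stated rule.

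A reader might also infer that the phase difference is biased towards less depletion in the demanding phase. That too goes beyond the evidence. Losing the two most depleted women is already close to a worst case, yet with the cited SDs the shift is at most about a tenth of the cited difference over r from 0 to 0.7, and it reverses above r of about 0.52.

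Non-completion may be rare: the women exercise habitually, the session is moderate and the workload is adjusted. The background statement on endurance concerns exercise to exhaustion, which is a different task. The two consent passages could describe one process. The study is a pilot, and for the full cited effect eight women would still give more than 90% power.

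These points limit the size of the concern. They do not remove it: later phases go uncollected after an event that the protocol's own rationale links to outcome and phase, and that is fixed in the protocol rather than left to an analysis plan.

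**Conclusion.** The concern holds in a limited form. The removal rule ends collection of remaining phases after an event that, on the protocol's reasoning, is related to glycogen and cycle phase. The women seen in all phases may therefore be selected, and the contrast may be biased. The size and sign depend on the non-completion rate, the strength of the link and the between-phase correlation, none of which is given.

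The firmer cost is lost information. It rests on assumed rates of 5–10% per session and, for the unused earlier visits, on a complete-case ANOVA that is likely but not written. It matters little if the liver effect is as large as the cited muscle effect, and clearly if it is half that size; section 8 itself says that no data exist on menstrual cycle effects on liver glycogen.

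**What to change.** The changes concern data handling only.

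- State that removal or withdrawal does not take validly measured visits out of the analysis, subject to one consent rule.
- Replace the ANOVA with a linear mixed model: participant as random effect; phase, exercise and their interaction as fixed effects. It uses women with fewer than four visits.
- Record minutes and work completed at each session, and report non-completion by phase. For a pilot this is useful in itself.
- Give a completers-only analysis as sensitivity.
- Reconcile Recruitment, Visits 2–5 and Discontinuation on the use of data from women who leave or are removed.
- Reconcile the removal rule with the study's need for data in every phase, and the two descriptions of the session, since completion cannot be judged until there is one. Which rule or session applies is for the investigators; this review proposes none.

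The cost is protocol and consent wording and slightly more analysis work; SPSS can fit the model. The downside is reliance on a missing-at-random assumption. If non-completion depends on depletion in the very session that was not measured, the mixed model reduces the problem but does not remove it, and it cannot replace visits that were never made.

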#### Sample handling

Samples will be stored in a linked anonymised format and labelled using a combination of study reference, unique study identifier and cross referenced with location code numbers to permit accurate linkage to study data and the consent form. The master database will be held by the study investigators in a password encrypted file.

Blood samples will be processed in the Nottingham Digestive Diseases Centre (NDDC) laboratories, University of Nottingham (located in the QMC) or SPMIC laboratories (on University Park Campus). Samples will be

transported from SPMIC following local standard operating procedures and stored securely in the NDDC laboratories at -80°C prior to analysis. The analysis of samples will take place either in the NDDC laboratories, University of Nottingham or else samples will be shipped to commercial providers for specialist analyses with a material transfer agreement arranged.

Once the study is completed and analysis has taken place, any residual samples will be stored within the Nottingham Digestive Diseases Centre Biomedical Research Unit Research Tissue Bank for future research (DI [name]- Licence Number 12265) if participants are agreeable and sign the optional clause on the consent form. Where participants do not agree to the future use of the samples, they will be destroyed in accordance with the Human Tissue Act, 2004.

Standard operating procedures (SOPs) will be followed for all laboratory assays to ensure the high quality and reliability of our generated data.

## Discontinuation/ withdrawal of participants from study

Participants may be withdrawn from the trial either at their own request or at the discretion of the Investigator. The participants will be made aware that this will not affect their future care. Participants will be made aware (via the information sheet and consent form) that should they withdraw the data collected to date cannot be erased and may still be used in the final analysis.

## Definition of end of study

The end of participant involvement in the study is at the end of the MR scanning visit.

#### **Expenses and benefits**

This study requires participants to attend 5 visits in total, 1 initial visit and 4 weekly study visits. Each visit will last a full morning, requiring blood sampling and moderate exercise for one hour. An appropriate inconvenience allowance for this commitment of £75 per visit will be offered, and a further £25 on completion of the study, equalling a total of £400.

# 6. INTERVENTION(S) & DRUG ADMINISTRATION

# a) Drug/Substance/Intervention 1

Name of drug/ substance/	Moderate exercise
intervention to be used	
Formulation and route of	Wmax determined using incremental workload increases
administration for study	
Dose and route of	60 minutes at 70% maximum heartrate
administration for study	
Duration of treatment for	1 x 60 minute of moderate exercise on each of 4 weekly visits
study	
Licence status of this	N/A
drug/substance	
Usual indication	N/A
Usual dose	N/A
Usual duration of treatment	N/A
Where will drug/ substance be sourced from?	
Where will drug/substance be stored?	
How will drug/substance be dispensed?	

How will the drug/ substance	
be prepared by the	
researchers for use in this	
study?	

#### 7. SAFETY

# a) Definitions

Adverse Event (AE)	Any untoward medical occurrence in a participant to whom a substance has been		
	administered, including occurrences which are not necessarily caused by or related		
	to that substance.		
Adverse Reaction (AR)	An untoward and unintended response in a participant to a substance, which is		
	related to any dose administered to that participant.		
	A causal relationship between the administered substance and an AE is at least a		
	reasonable possibility, i.e. the relationship cannot be ruled out.		
	All cases judged by either the reporting medically qualified professional or the		
	Sponsor as having a reasonable suspected causal relationship to the study		
	intervention qualify as adverse reactions.		
Serious Adverse Event	A serious adverse event is any untoward medical occurrence that:		
(SAE)	results in death		
	is life-threatening		
	requires inpatient hospitalisation or prolongation of existing hospitalisation		
	results in persistent or significant disability/incapacity		
	consists of a congenital anomaly or birth defect.		
	Other 'important medical events' may also be considered serious if they jeopa		
	the participant or require an intervention to prevent one of the above		
	consequences.		
	NOTE: The term "life-threatening" in the definition of "serious" refers to an event		
	in which the participant was at risk of death at the time of the event; it does not		
	refer to an event which hypothetically might have caused death if it were more		
	severe.		
Serious Adverse Reaction	An adverse event that is both serious and, in the opinion of the reporting		
(SAR)	Investigator, believed with reasonable probability to be due to one of the study		
	treatments, based on the information provided.		
Suspected Unexpected	A serious adverse reaction, the nature and severity of which is not consistent with		
Serious Adverse Reaction			
(SUSAR)	characteristics (SmPC).		

